### **4.2 Two Week Screening Period**

#### **4.2.1 Medication Regimen Monitoring (≥14-Day Period)**

The anti-hypertensive drug regimen of the subject will be monitored for a period of at least 14 days at baseline. Medication logs will be provided for the subject to record their daily anti-hypertensive drug regimen during the monitoring period. Upon the completion of the monitoring period (≥14 days), the subject will return to the study center with the medication logs for the continued baseline evaluation.

The medication log will be reviewed to assess the subject's compliance with their current medication regimen. The clinical investigation does allow the inclusion of subjects that are not on guideline based therapy due to intolerance. Intolerance to medications is defined as a relative or an absolute contraindication to an anti-hypertensive medication. This assessment will be left to the discretion of the Study Investigator.

It is recommended that the subjects maintain their enrollment anti-hypertensive regimen for a minimum of 180 days post procedure unless clinically necessary for changes to occur.

Investigators will urge subject compliance to prescribed medical regimen at the onset of the 14 day monitoring period and throughout the trial. If the subject is non-compliant without medical rationale, the subject may be excluded.

#### **4.2.2 Ambulatory Blood Pressure**

To ensure proper patient selection for inclusion in the study subjects must have a daytime mean Ambulatory Blood Pressure (ABP) measurement of > 135 mmHg within 90 days prior to procedure.

If there is a change in medication after ABP assessment an additional ABP assessment is required to determine eligibility. In addition to the daytime mean ABP, the night time mean, and 24 hour average ABP value will be collected. When using ABP ensure that at least two measurements per hour are taken during the person's usual waking hours (for example, between 08:00 and 22:00) and 1 measurement per hour are taken during the person's usual night time hours. The average value of at least 14 measurements taken during the person's usual waking hours should be used for calculation of mean daytime value.

Measurements should be taken according to Standard Joint National Committee VII Guidelines ESC and ESH Guidelines, refer to Appendix B for 24 Hour Ambulatory Blood Pressure instructions.

The ABP can be taken during the two week screening period but must be repeated if there are medication changes. .

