## 4 Procedures

Table 1: Data/CRF Collection

Visit	Enrollment / Baseline	Confirmatory	Procedure	Discharge <72 hrs	1M ±14d	6M ±30d	12M ±60d	24M ±60d	36M ±60d	48M ±60d	60M ±60d
PIS & PIC	X										
Inclusion/Exclusion	X	X-review for changes									
Medical History	X	X-review for changes									
Office Blood Pressure	X	X		X	X	X	X	X	X	X	X
Physical Assessment	X	X-review for changes		X	X	X	X	X	X	X	X
24-h Ambulatory Blood Pressure	X-performed w/in 90 days of procedure	X-repeat if there are medication changes				X	X	X	X	X	X
Discharge Blood Pressure				X*							
***Echocardiography (TTE)		X			X	X		X			X
NYHA Assessment	X				X	X		X			X
Serum creatinine		X				X	X	X			X
Estimated GFR		X				X	X	X			X
Hemoglobin A1c		X				X					
Fasting Glucose		X				X					
Fasting Insulin		X				X					
Urine albumin-to-creatinine ratio		X				X		X			X
Medications Log	X	X-review for changes		X	X	X	X	X	X	X	X
Quality of Life questionnaire		X			X	X		X			X
Renal Artery Anatomy Evaluation		X – if not performed w/in 90 days	X			X		X			X
Pregnancy Test (urine / blood)		X									
Renal Denervation Procedure			X								
Adverse Event	**	**	**	**	**	**	**	**	**	**	**
CIP Deviation	**	**	**	**	**	**	**	**	**	**	**
Withdrawal/Termination			**	**	**	**	**	**	**	**	X
(*) monitored every 4 hours post procedure until discharge, or for a maximum of 24 hours (**) as applicable (***) Echo will be performed at 6 preselected sites											

SJM CONFIDENTIAL AND PROPRIETARY

© 2012 – St. Jude Medical Cardiovascular Division: All rights reserved. No portion of this work may be reproduced in whole or in part without the express written permission of St. Jude Medical Cardiovascular Division.  
 Clinical Investigational Plan: EnligHTN II

SJM CONFIDENTIAL AND PROPRIETARY

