## 4.1 Enrollment/Baseline Visit

Prior to enrollment in the clinical investigation, site personnel will evaluate potential candidates by reviewing the patient medical records against the inclusion and exclusion criteria. It is expected that the medical records will contain adequate and accurate information to determine if the patient meets these criteria.

If a patient meets all inclusion criteria and does not meet any of the exclusion criteria, the patient shall be eligible for the investigation.

If the patient agrees to participate, the study site personnel shall follow the informed consent process set forth in Section 5.2 and obtain the signature and date from the patient on the approved Patient Informed Consent (PIC) form (previously approved by Ethics Committee and the Sponsor). If the patient does not sign and date the Patient Informed Consent (PIC), they cannot participate in the investigation. No further CIP required activities are allowed.

A patient becomes a subject once he/she has been fully informed about the investigation, has agreed to participate, signed & dated the PIC and therefore has been enrolled in the investigation.

NOTE: As soon as the subject signs the Patient Informed Consent, adverse events need to be reported according to the guidelines mentioned in Section 5.3.

The EC should be notified appropriately about any CIP deviations with regards to obtaining informed consent.

If new information becomes available during the clinical study that can significantly affect a patient's future health and medical care, that information will be provided to the patient(s) in written form.

The following information will be collected at the baseline visit either from hospital records or through patient interaction documented in the hospital records. All baseline activities are performed after the patient is enrolled in the investigation. Tests and procedures required at baseline can be completed within 90 days of enrollment but must be completed prior to procedure.

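### The baseline ambulatory BP may be recorded at or near the start of the drug monitoring, so early adherence gains can appear as ambulatory BP reduction

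*Combined protocol and SAP*

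**What the plan says.** **Timing of the ABP.** For eligibility, Section 4.2.2 says subjects "must have a daytime mean Ambulatory Blood Pressure (ABP) measurement of > 135 mmHg within 90 days prior to procedure". It adds: "The ABP can be taken during the two week screening period but must be repeated if there are medication changes". Table 1 (Section 4) enters the 24-hour ABP in the Enrollment/Baseline column as "X-performed w/in 90 days of procedure" and in the Confirmatory column only as "X-repeat if there are medication changes". Section 4.1 says: "Tests and procedures required at baseline can be completed within 90 days of enrollment but must be completed prior to procedure". Section 4.3 lists the ABP among items to be reviewed at the confirmatory visit. It calls for a new recording after a medication change, or when a subject who failed eligibility is re-evaluated.

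**Drug monitoring.** Section 4.2.1 says: "The anti-hypertensive drug regimen of the subject will be monitored for a period of at least 14 days at baseline". It continues: "Investigators will urge subject compliance to prescribed medical regimen at the onset of the 14 day monitoring period and throughout the trial". On poor compliance it says: "If the subject is non-compliant without medical rationale, the subject may be excluded".

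**Office BP.** Section 3.6.1 requires office systolic pressure of at least 140 mmHg at the confirmatory visit. Section 4.3 and Table 1 have it measured again there in every subject.

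**Analysis.** Section 7.4.2.3 computes ABP change in the same way as the office change in Section 7.4.1: follow-up against baseline in subjects who have both values, summarised by mean and SD. Neither section says which pre-procedure reading is the baseline. The study is single-arm (Section 3.3) and has no hypothesis test (Section 7.2).

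**The concern.** The two pressure measures are treated differently. The office reading that qualifies a subject comes after at least two weeks of logged and urged drug-taking. The ambulatory reading need not. It may be made on the day the log is handed out or in the first days of the period, and it then stands unless the medication changes. The natural meaning of a medication change is a change of regimen. A subject who starts to take an unchanged prescription properly triggers no repeat.

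Two things follow. First, a fall in ambulatory pressure that comes from better drug-taking during the monitoring lies after the baseline reading, so it enters the change that will be read as the performance of the device. Without a control arm or an adherence adjustment, nothing later in the plan takes it out. Second, a subject whose daytime mean would be 135 mmHg or lower once the drugs are taken can still enter on the earlier recording.

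**Working it through.** There is no figure of the plan to reproduce. Section 7.2 gives about 500 subjects without an effect size, SD, alpha or power. The check is therefore a reading of the timing rules, followed by an illustration of size.

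**1. Order of events for a subject whose prescription does not change**

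| Step | Office systolic BP | Ambulatory BP |
|---|---|---|
| Enrollment/Baseline visit | measured | may be recorded (Table 1) |
| Start of monitoring, compliance urged (4.2.1) | – | may be recorded (4.2.2) |
| During the ≥14 days | – | may be recorded (4.2.2) |
| Confirmatory visit (4.3) | measured again in all; must qualify (3.6.1) | existing value reviewed only |
| 6 months | measured | measured |

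The ABP can fall at either end of the monitoring period. No rule asks for the end.

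**2. Is there another trigger for a repeat?** Section 4.3 and Table 1 give two: a medication change, and re-evaluation of an ineligible subject. Better adherence is neither. Exclusion for non-compliance is optional under Section 4.2.1, and that section attaches no repeat ABP to it.

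**3. Is the gain removed in the analysis?** No. For each subject the change is follow-up minus baseline. If a subject's pressure falls by d through better drug-taking after the baseline recording and before the end of monitoring, and the gain is kept, d is part of the change.

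**4. Size.** Let f be the share of subjects whose drug-taking improves between the ABP recording and the end of monitoring, and d their mean fall. Then

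shift in mean ABP change = f × d.

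The documents give neither f nor d, so both are assumptions:

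- f = 10%, d = 5 mmHg: 0.10 × 5 = 0.5 mmHg
- f = 20%, d = 10 mmHg: 0.20 × 10 = 2.0 mmHg
- f = 30%, d = 15 mmHg: 0.30 × 15 = 4.5 mmHg

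This spread reflects the assumed inputs and is not an estimate. Only gains made inside that short interval count towards f.

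**5. Comparison with sampling error.** With n = 500 (Section 7.2, taking every subject to have both recordings) and an assumed SD of the change of 12 to 20 mmHg, the 95% half-width is 1.96 × SD / √500:

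- SD 12: 1.96 × 12 / 22.36 = 1.05 mmHg
- SD 20: 1.96 × 20 / 22.36 = 1.75 mmHg

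A shift of 2 mmHg, if it occurred, would exceed the sampling error of the overall mean. A larger sample would not reduce it.

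**The case against.** The strongest reply is that the sentence in Section 4.2.2 places the ABP during the screening period, and that compliance is urged from the onset of that period. A recording made under that sentence therefore does not precede the urging. This stands as far as that sentence goes. Table 1 and Section 4.1, however, also allow the recording at the baseline visit itself, and a recording on the first day still precedes most of any gain.

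A reader might infer from the 90-day window alone that the ABP can lie up to 90 − 14 = 76 days before monitoring starts. The documents do not support that. Section 4.1 has baseline activities follow enrollment, Section 4.2.1 puts the monitoring at baseline, and Section 3.6 caps the gap from baseline to procedure at 90 days. No passage describes a long gap between the ABP and the start of the log.

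There are partial safeguards. A stable regimen is an inclusion criterion, the log is reviewed, non-compliant subjects may be excluded, and office pressure must still qualify after monitoring. These limit the number of subjects affected. None of them renews the ABP in a subject whose drug-taking improves on an unchanged regimen.

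Finally, ABP change is a secondary, descriptive measure. That lowers the weight of the point. It does not remove the bias from the reported mean.

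**Conclusion.** The point holds in a limited form. The plan permits, but does not require, a baseline and qualifying ABP made before or early in the monitored drug-taking, while it holds office pressure to a reading afterwards. Adherence gained between that recording and the end of monitoring can pass for ambulatory BP reduction, mainly at 6 months, and some subjects may qualify on a recording made before drug-taking was checked.

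The size is unknown. The 2 mmHg example rests on an assumed 20% of subjects improving by an assumed 10 mmHg. The share recorded early is not known either.

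Two stronger readings go beyond the documents:

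- A reader might set such a shift against the 9.9 mmHg ambulatory fall of the feasibility study (Section 2) and call it a percentage of the device effect. The numerator is assumed, and the denominator is a 3-month result in a study of 46 patients. If f counted all adherence gained over the months after enrollment, it would also include gains that the date of the ABP cannot affect.
- A reader might infer a one-sided bias at every visit to 60 months. Adherence may also wane over five years, and Section 4.2.1 only recommends an unchanged regimen for at least 180 days, so the direction at later visits is not established.

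This is a worthwhile, low-cost improvement to a secondary measure. It is not a flaw in the primary objective.

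**What to change.** - **Section 4.2.2 and Table 1:** time the qualifying ABP at the end of the ≥14-day monitoring period, around the confirmatory visit, with the log reviewed alongside it. Move the mandatory entry in Table 1 to the Confirmatory column. An earlier recording may serve for pre-screening only. Section 4.3 would then check this reading.
- **Section 7.4.2.3:** name that reading as the baseline for every ABP change. Section 7.4.1 needs the same clarity for office pressure, which has both a baseline-visit and a confirmatory-visit value.

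**Cost.** The change is one of protocol wording and moves a recording that is already scheduled. Subjects with an earlier ABP repeat one non-invasive recording, and a few may no longer qualify.

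**Limit.** The change removes only adherence gains made up to the new recording. Compliance is urged throughout the trial and there is no control arm, so later gains stay in the estimate. The report should say so when it presents the ABP change.

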#### **4.3 Confirmatory Visit**

After the two week screening period the subject will return to the Study Center for the confirmatory visit.

The following items will be reviewed or performed at the confirmatory visit to ensure there have been no changes prior to moving forward with the EnligHTN Renal Denervation procedure.

- Inclusion / exclusion criteria
- Medication logs
- Medical history & physical assessment
- Office Blood Pressure measurements will be recorded as the average Blood Pressure of three measurements
- Review of daytime mean Systolic Ambulatory Blood Pressure (must be repeated if there are medication changes)

If the subject does not meet eligibility after baseline and 2 week screening period they may be re-evaluated. The Office Blood Pressure, Medication log and the Ambulatory Blood Pressure will need to be repeated if it is determined the subject could be re-evaluated.

##### **4.3.1 Blood and Urine Analysis**

Blood and urine samples will be collected and analyzed as listed below.

- Serum Creatinine
- Estimated GFR (eGFR)

---

SJM CONFIDENTIAL AND PROPRIETARY

© 2012 – St. Jude Medical Cardiovascular Division: All rights reserved. No portion of this work may be reproduced in whole or in part without the express written permission of St. Jude Medical Cardiovascular Division.

Clinical Investigational Plan: EnligHTN II

- Hemoglobin A1c
- Fasting glucose
- Fasting insulin
- Urine albumin-creatinine ratio
- Pregnancy test (only at baseline)

A true numeric value for the estimated GFR must be provided. If your local laboratory does not report the eGFR value beyond 60 mL/min/1.73 m^2 the center should use a sponsor-approved calculation tool to generate the value. The sponsor will provide an approved website(s) for this calculation to study centers.

#### **4.3.2 Transthoracic-echocardiogram (TTE)**

Transthoracic-echocardiogram (TTE) examinations will be conducted at approximately 6 sites. Each site is responsible for performing the echocardiogram per each institutions standard of care echo protocol.

#### **4.3.3 NYHA Assessment**

NYHA Assessment will be evaluated at baseline and should be classified based on the definitions in Appendix C.

#### **4.3.4 Quality of Life Questionnaire**

EQ-5D 5L questionnaire will be completed at baseline.

#### **4.3.5 Baseline Renal Artery Anatomy Evaluation**

Adequate renal artery imaging is recommended to occur within 90 days prior to enrollment. Renal artery imaging by Duplex Ultrasound (U/S) should be performed to evaluate the subject's renal artery anatomy. Study investigators may consider requesting a computed axial tomography scan (CT scan) or utilize the procedural angiogram if the Duplex Ultrasound is inconclusive or shows any renal abnormalities.

Renal artery evaluation data collected will include but are not limited to:

- Type of evaluation - computed axial tomography (CT scan), duplex ultrasonography, angiography, Doppler, magnetic resonance (MR) angiography, or non-contrast MRI
- Length of artery(s)
- Diameter of artery(s)
- Number of main renal arteries
- Number of accessory renal arteries
- Presence and percent of stenosis
- Other abnormalities

---

SJM CONFIDENTIAL AND PROPRIETARY

## 4.4 Subject Group Assignment

Subjects who have met all of the baseline and enrollment criteria will be assigned to one of the following groups:

### 4.4.1 Group A: (minimum of 100 subjects)

- Office systolic Blood Pressure  $\geq 160$  mmHg
- Subject is taking  $\geq 3$  anti-hypertensive medications (including 1 diuretic), or subject has documented drug intolerance to 2 or more of the 4 major classes of anti-hypertensives (ACE/ARB, Calcium Channel Blockers, Beta Blockers, or diuretic) and is unable to take 3 anti-hypertensive drugs.
- Patient has an estimated GFR  $\geq 45$  mL/min per  $1.73 \text{ m}^2$  using the Modification of Diet in Renal Disease (MDRD) formula

### 4.4.2 Group B: (minimum of 50 subjects)

- Office systolic Blood Pressure  $\geq 140$  mmHg
- Subject is taking  $\geq 3$  anti-hypertensive medications (including 1 diuretic), or subject has documented drug intolerance to 2 or more of the 4 major classes of anti-hypertensives (ACE/ARB, Calcium Channel Blockers, Beta Blockers, or diuretic) and is unable to take 3 anti-hypertensive drugs.
- Patient has an estimated GFR  $\geq 45$  mL/min per  $1.73 \text{ m}^2$  using the Modification of Diet in Renal Disease (MDRD) formula

### 4.4.3 Group C: (minimum of 50 subjects)

- Office systolic Blood Pressure  $\geq 140$  mmHg
- Subject is taking  $\geq 3$  anti-hypertensive medications (including 1 diuretic), or subject has documented drug intolerance to 2 or more of the 4 major classes of anti-hypertensives (ACE/ARB, Calcium Channel Blockers, Beta Blockers, or diuretic) and is unable to take 3 anti-hypertensive drugs.
- Patient has an estimated  $\geq 15$  GFR  $< 45$  mL/min per  $1.73 \text{ m}^2$  using the Modification of Diet in Renal Disease (MDRD) formula

#### 4.5 Renal Denervation Procedure

The renal nerve ablation should be performed according to the EnligHTN™ Renal Denervation System Instructions for Use (IFU).

The renal denervation procedure should always be done with the aid of fluoroscopy. With the patient under local anesthesia, an introducer sheath will be inserted into the femoral artery using the standard percutaneous technique (modified Seldinger technique). A heparin bolus of 3000 to 5000 units will then be administered intravenously or per institution's standard of care. An 8 French guiding catheter sheath will be inserted to engage each main renal artery sequentially with the angiograms recorded. Images of the left and right main renal arteries will be recorded using the non-ionic contrast and the diameter and length of each of the main renal arteries will be measured.

Prepare the patient for standard electrosurgery. Select an appropriate basket size of the Basket Renal Denervation Catheter (small size for patient with renal artery diameter between 4mm and 6mm and large size for patient with renal artery diameter between 5.5mm and 8mm) should be chosen. The Basket Renal Denervation Catheter will be inserted with the tip of the catheter positioned proximal to the bifurcation of one of the main renal arteries and the corresponding images will be recorded. The basket on the Renal Denervation Catheter will then be opened, while the impedance of each electrode on the basket will be monitored. To begin the ablation, the "START" button on the RF Generator will be pressed with the impedance, temperature and RF energy delivery monitored and recorded during the process. The investigator will decide the location(s) and number of ablation sites/lesions (4 to 8 ablation sites/lesions are recommended) in the main renal artery. When the ablation procedure is completed in this main renal artery, the basket on the Catheter will be withdrawn from the artery with the Basket Renal Denervation Catheter fully closed. Images of the renal artery using the non-ionic contrast will be recorded. Any signs of renal artery irregularities (vasospasm, stenosis or dissection) will be checked.

The same renal artery ablation procedure will be repeated for the other main renal arteries. When the ablation procedure for the main renal arteries are also completed, the basket on the Renal Denervation Catheter will be withdrawn from the artery with the Basket Renal Denervation Catheter fully closed and the catheter will be visually inspected and flushed with heparinized saline. Finally, the sheath will be removed according to the center's standard of care.

Procedural data collected will include but is not limited to:

- EnligHTN™ Renal Denervation System device information
- Guiding catheter used – manufacture
- Number of arteries ablated
- Number of ablations performed
- Device settings
- Procedure time
- Ablation time
- Fluoroscopic time
- Volume of contrast media

---

SJM CONFIDENTIAL AND PROPRIETARY

© 2012 – St. Jude Medical Cardiovascular Division: All rights reserved. No portion of this work may be reproduced in whole or in part without the express written permission of St. Jude Medical Cardiovascular Division.

Clinical Investigational Plan: EnligHTN II

## 4.6 Product Training

All physician users will undergo product training prior to initial human use and at the time of initial human use there is an expectation that each site will be proctored by a SJM clinical specialist until there is demonstration of product usage per the IFU and site ancillary procedural staff have been trained on the ablation generator.

